Appendix IV – Mayo Patient Survey

List of Abbreviations

3DCRT	3-D Conformal Radiation Therapy
AE	Adverse Event/Adverse Experience
CBCT	Cone Beam CT
CFR	Code of Federal Regulations
CRF	Case Report Form
CTV	Clinical Target Volume
DSMB	Data and Safety Monitoring Board
FDA	Food and Drug Administration
GCP	Good Clinical Practice
HIPAA	Health Insurance Portability and Accountability Act
IBTR	Ipsilateral breast tumor recurrence
IMRT	Intensity Modulated Radiation Therapy
IRB	Institutional Review Board
MRI	Magnetic Resonance Imaging
PHI	Protected Health Information
PI	Principal Investigator
PTV	Planning Target Volume
QOL	Quality of Life
RBE	Relative biologic effectiveness
RT	Radiation Therapy
SAE	Serious Adverse Event/Serious Adverse Experience
SOP	Standard Operating Procedure
XRT	X-ray Radiation Therapy

SCHEMA

N=110 patients

Study Design: This is an open label phase III randomized controlled trial to determine the safety of 5 fraction vs 15 fraction pencil beam scanning proton radiotherapy to the whole breast alone after breast conserving surgery. Proton therapy is recognized as a standard option for the delivery of radiotherapy for breast cancer.

1.0 Background

1.1 Benefits and Risks of Adjuvant Radiotherapy

Breast conserving therapy (BCT), consisting of partial mastectomy, followed by whole breast radiotherapy, is a widely accepted standard of care and the preferred local treatment approach for many women with breast cancer. Women opting for breast conserving therapy have improved body image, quality of life, and sexual function^{1,2}.

Six randomized studies with long term follow up have established the equivalent overall survival of breast conserving therapy to mastectomy³⁻⁸. The breast radiotherapy component of BCT has been shown to improve rates of local control, reduce distant recurrence, and improve survival^{9,10}. Despite the strong evidence for breast conserving therapy, there is underutilization of both breast conserving surgery¹¹ and adjuvant radiotherapy¹². While many factors likely contribute, convenience of therapy, access to treatment facilities¹³, cost, and perceived toxicity of therapy may all represent barriers to radiation therapy¹⁴.

Survival rates for breast cancer are high, as most women diagnosed will not die of their disease¹⁵. As such, recent oncologic emphasis has highlighted survivorship, with strategies aimed to improve treatments, treatment-related adverse effects, and long term quality of life^{16,17}. These improvement strategies aim to improve the therapeutic ratio, with enhanced benefits of therapy, reduced toxicity, or both.

Careful study of photon breast radiotherapy techniques has highlighted potential long term toxicities and opportunities to enhance the therapeutic ratio. Data demonstrating late cardiovascular toxicity, particularly for women with left-sided tumors, and risk of secondary malignancy have garnered particular attention in recent years,¹⁸ and these toxicities have been shown to partially offset the cause-specific survival benefit of adjuvant radiotherapy^{9,19}.

Cardiovascular toxicity has been studied in great detail and appears to be primarily mediated by a vascular etiology, likely with macro- and microvascular contributions. Amongst women undergoing adjuvant radiotherapy for breast cancer, Correa and colleagues²⁰ demonstrated a likelihood of left anterior descending artery (LAD) stenosis in excess of what would be expected, providing indirect evidence of radiation-mediated coronary artery disease. Darby and co-authors¹⁹ found that the risk of major coronary events (myocardial infarction, coronary revascularization, or death from ischemic heart disease) was related to the mean heart dose and not the LAD, suggesting a microvascular etiology. Radiation related cardiovascular toxicity is likely multifactorial, and multiple dose-volume relationships are likely important risk factors of subsequent cardiac disease, including dose to the LAD, heart (mean heart dose and volumetric parameters such as V₂₅) and left ventricle²¹. Efforts to minimize cardiac exposure to radiotherapy, while studying the potential dose relationships are of utmost importance, particularly in the

modern systemic therapy era, which now includes more agents with known cardiac effects, including anthracyclines and trastuzumab.

Adjuvant radiotherapy for breast cancer has also been associated with an elevated risk of developing a secondary malignancy⁹. Specifically, radiotherapy is associated with increased risk of developing and dying from ipsilateral lung cancer^{9,22}. Radiotherapy is also associated with increased risk of contralateral breast carcinoma⁹. This is a result of inadvertent and unnecessary dose delivered to normal organs adjacent to disease targets.

Radiotherapy to the breast may also result in breast fibrosis, breast shrinkage, worsening of cosmesis, and arm and shoulder pain.^{23,24,25} There is evidence that these late effects are potentially dose dependent.

In summary, breast conserving therapy is a standard of care and offers many advantages to women, and radiotherapy is necessary to achieve optimal oncologic outcomes. However, in the modern era of enhanced technology and improved emphasis on survivorship, there is strong rationale for the development and evaluation of novel strategies that reduce unnecessary radiation exposure to normal tissue, as well as novel dose and fractionation regimens which may improve the therapeutic ratio, while reducing costs and increasing convenience of delivery. We propose a prospective phase III trial that will evaluate the use of hypo-fractionation with either x-rays or proton therapy

1.2 Rationale for Proton Therapy in Breast Cancer

Enhanced radiotherapy delivery techniques may enable better treatment delivery with reduced toxicity. Proton therapy, in particular, may reduce treatment toxicity, as there is less non-target tissue exposed to radiation therapy. Relative to photons, protons have fundamental physical advantages in the treatment of tumors adjacent to radiosensitive normal structures. By exploiting the Bragg peak of proton beams, target tissues may be covered with a similar or better dose distributions as with photons, with reduced unintended dose to other tissues, including reduced integral dose^{26,27}. Thus, interest in the possible benefits of breast cancer radiotherapy with protons is emerging, with hopes of being able to maintain or improve the locoregional control and cause-specific survival, with potential to reduce toxicity.

Clinical experience with proton beam radiotherapy (PBT) in the treatment of breast cancer patients remains limited, though increased institutional experiences are reported, and a multi-center randomized study in node positive patients has been initiated (CITE PCORI). A recent review examined published experience with PBT for breast cancer²⁸. This report highlights the limited published clinical experience with proton beam for breast cancer, in particular demonstrating very little data for whole breast radiotherapy without regional nodal treatment. The two such cited studies were retrospectively planned proton versus plan comparisons, rather than clinical experience, yet each supported a dosimetric advantage to PBT for left sided breast cancer patients undergoing BCT, with a reduction in mean heart dose, coronary artery dose, and ipsilateral lung dose^{29,30}.

Clinical experience in the node positive setting is published. MacDonald et al³¹ recently published early outcomes for a small cohort of 12 patients treated with proton radiotherapy following mastectomy. All patients received chest wall irradiation and eleven received radiotherapy to the supraclavicular, level 3, and internal mammary lymph

node chains. Nine patients had grade 2 skin toxicity and 3 patients had grade 1 skin toxicity. There was no \geq grade 3 skin toxicity reported. During treatment 6 patients experienced grade 1 fatigue, 5 patients experienced grade 2 fatigue, and there was one incident of grade 3 fatigue. By 4 weeks follow-up fatigue had completed resolved in all but 1 patient who continued to have grade 1 fatigue. There were no reported cases of pneumonitis. The average mean dose to the heart was 0.44 Gy and the average mean V20 of the lung was 12.7%. Cuaron et al. recently reported the results of treatment of the largest cohort of patients treated with proton therapy for breast cancer.³² Four patients were treated after lumpectomy, 24 after mastectomy (including 14 patients with implant reconstruction and 1 patient with autologous reconstruction) and 2 patients received proton therapy after wide local excision of a chest wall recurrence. Grade 2 dermatitis occurred in 20 patients (71.4%), 8 of whom (28.6%) also experienced moist desquamation. Grade 2 esophagitis was observed in 8 patients (28.6%). There was 1 grade 3 reconstructive complication. The median mean heart dose was 0.88Gy and the median V20 of the ipsilateral lung was 16.5%. This early data suggests that post-mastectomy and post-lumpectomy proton therapy is feasible and well tolerated with reduced dose to the heart and lung, warranting further study.

In addition to the clinical experience in the locally advanced setting, several institutions have examined PBT for partial breast radiotherapy. One such initial report showed high rates of acute skin toxicity, pigmentation changes, and worse physician reported cosmesis³³. However, the planning techniques reported therein, including passive scatter and a single beam treated per day for many, possibly contributed to these outcomes. A larger series from Loma Linda with 60 month follow up and 100 patients reported good to excellent cosmetic outcome in >90% throughout 5 years of follow up³⁴. No patient had acute grade 3 or higher skin toxicity. Ispilateral tumor recurrence rates at 5 years were 3%. In addition to differences in dose and technique, once daily treatments were used.

Much of the published PBT experience is with passively scattered protons. A concern with this technique is the high entrance skin dose which may be associated with higher skin toxicity and adverse cosmesis.³³ This higher skin dose may be of particular concern in patients who undergo breast conserving surgery. Scanning beam proton therapy, the technique proposed in this study, offers potential advantages over passively scattered protons including increased conformality with even less unintended dose to normal tissues, including the skin.³⁵ However, this technique is also potentially more sensitive to uncertainties including inter-fractional as well as intra-fractional motion which must be taken into account in treatment delivery. Rigorous clinical studies of scanning beam proton therapy are needed to determine the disease control and toxicity outcomes with this technique and to determine whether the physical dose advantages of proton therapy translate to substantial and lasting improvements in patient outcome.

In summary, there is strong interest in prospectively designing and understanding proton therapy in breast cancer. Data for proton therapy in breast cancer are limited, particularly in the intact breast setting, yet there is compelling rationale for study of proton beam therapy for breast cancer to reduce radiation dose to non-target tissue and potentially improve outcomes for breast cancer survivors. In view of the need to gain experience, a clinical study is supported.

1.3 Rationale for Hypofractionation in Breast Cancer

Hypofractionated, or shorter course, radiotherapy presents an opportunity to enhance access to care, increase convenience and acceptability of therapy, while reducing cost and potentially improving toxicity. Although the use of proton therapy for breast cancer is still in early development, concerns regarding proton therapy have primarily been related to costs, rather than technical feasibility in the clinic. Proton therapy departments are more expensive to build as they require huge accelerators to deliver the beam. While proton therapy is considered more expensive than conventional forms of radiation, cost-benefit studies have suggested cost-effectiveness in the long term due to decreased long term toxicity.³⁶⁻³⁸ An important driver of cost of both photon and proton radiotherapy is the number of treatments delivered to individual patients, with shorter courses resulting in lower expenditures³⁹. Studies are needed to evaluate whether equivalent or improved outcomes can be achieved with shorter courses of therapy.

Furthermore, the optimal dose and fractionation regimen for whole breast irradiation, whole breast and regional nodal irradiation, and postmastectomy radiotherapy remains unknown. While there is widespread clinical experience with standard fractionation, newer preclinical and clinical data support a shorter course of radiotherapy.

For fraction sizes up to approximately 8 Gy, The linear-quadratic formula model is the preferred method of predicting the relationship between fraction size and tissue response of varying radiotherapy regimens. Its origins stem from what has been described as a two-component survival curve for mammalian cells represented by the curvilinear dose-response curve for the log of cell survival.⁴⁰ In it, the biologically effective dose (BED) of a given fractionation regimen is related to the α/β ratio in the following equation, where α represents the \log_e of the cells killed per gray and β is the \log_e of the cells killed per gray squared:

$$\text{BED} = nd(1 + d/\alpha/\beta)$$

d = dose per fraction
 n = # of identical fractions

The ratio of α/β is the dose at which the linear and quadratic components of cell killing are the same. In general, early-responding tissues such as skin desquamation have a high ratio whereas late-responding tissues such as dermal contraction have a low ratio and are very sensitive to increases in fraction size.⁴¹

Emerging evidence suggests that the α/β ratio of breast cancer may be low and more in line with that of late responding tissues and therefore breast cancer patients may not benefit from prolonged fractionation regimens.^{42,43} Indeed, the most robust data to date suggesting this relationship has come from the UK Standardization of Breast Radiotherapy (START) trials, two modern breast cancer randomized controlled trials examining various fractionation regimens that have recently been reported with 10-year follow-up. In START-A, a regimen of 50Gy in 25 fractions to the whole breast over 5 weeks was compared with 41.6Gy or 39 Gy in 13 fractions over 5 weeks. There was no significant difference in local-regional relapse between the 41.6Gy and 50Gy regimens (6.3% vs 7.4%, p=0.65) or the 39Gy and 50Gy regimens (8.8 vs 7.4%, p=0.41).²⁴ Moderate or marked breast induration, telangiectasia, and breast edema was less common in the 39Gy group compared with the 50Gy group, and rates of these toxicities were no different between the 41.6Gy and 50Gy groups. The treatments in each arm were given over the same time period, enabling an estimate of sensitivity of breast cancer to changes

in fraction size that was not confounded by differences in treatment time. An α/β ratio for local-regional relapse of breast cancer was determined from a meta-analysis of START-A and the START pilot trial (349 events, 3646 women) as 3.5 Gy (95% CI 1.2-5.7). The α/β ratio for normal tissue toxicity endpoints included 3.5Gy (95% CI 0.7-6.4) for breast shrinkage, 4Gy (2.3-5.6) for breast induration, 3.8Gy (1.8-5.7) for telangiectasia, and 4.7 Gy (2.4-7.0) for breast edema, suggesting that normal tissue toxicity may not be reduced and may even be increased when breast cancer radiotherapy fractionation regimens are prolonged with small daily fractions.

Further evidence supporting hypofractionated regimens for breast cancer came from the START-B clinical trial, in which 50Gy in 25 fractions over 5 weeks was compared with 40Gy in 15 fractions over 3 weeks. There was no difference in local-regional relapse at 10 years between 40Gy and 50Gy groups, (4.3% vs 5.5%, $p=0.2$) but breast shrinkage, telangiectasia, and breast edema were significantly less common with the shorter fractionation regimen. These data are consistent with the results of the Canadian hypofractionation trial which compared 42.5Gy in 16 fractions in 3.2 weeks to 50Gy in 25 fractions over 5 weeks and suggest that the use of smaller fractions is of no benefit in terms of tumor control or reduction in toxicity, at least in the doses used in these studies, and may potentially be deleterious.^{24,44} Interestingly, if one applies an α/β ratio for both normal tissue toxicity and tumor control of 3.5 from START-A, the 40Gy regimen from START-B is equivalent to 44.9Gy in 2 Gy fractions. This may imply that differences in overall treatment time of a course of radiation therapy may be more important than originally thought, potentially allowing further dose reduction when fractionation regimens are shortened, as we propose here.^{45,46}

Other moderate hypofractionated radiotherapy treatments support excellent local control and comparable toxicity outcomes. Ahlawat et al, reported on 83 women treated after breast conserving surgery 36.63 Gy in 11 fractions of 3.33 Gy per day, with a 4 fraction boost of an addition 3.33 Gy⁴⁷. Three year local recurrence free survival was 95.9%, and breast cosmesis was good or excellent in 94% of evaluable patients.

In the FAST trial, 915 women aged ≥ 50 years with node negative early breast cancer after wide local excision were randomly assigned to receive 50 Gy in 25 fractions of 2.0 Gy over 5 weeks versus 28.5 Gy or 30Gy in 5 fractions once weekly fractions of 5.7 Gy or 6.0 Gy. Three-year rates of physician-assessed moderate/marked adverse effects in the breast were 17.3% (13.3-22.3%, $p<0.001$) for 30Gy and 11.1% (7.9-15.6%, $p=0.18$) for 28.5Gy compared with 9.5% (6.5-13.7%) after 50Gy.⁴⁸ Further follow-up is needed to determine local control of these three regimens but promisingly at a median follow-up of 37.3 months in survivors, only 2 ipsilateral breast recurrences were noted.

Rovea, et al reported outcomes with 5 fractions of 6 to 6.5 Gy delivered once weekly for 291 elderly patients⁴⁹. 5 year Local control was excellent at 98%. Late skin fibrosis was Grade 2 in 4.2% and grade 3 in 1.4%. Breast edema was low, at 7%, 4.2%, and 1.4% for Grade 1, 2, and 3, respectively. Good to excellent cosmetic outcome was reported in 86.4%. Similarly, favorable acute toxicity results were reported among 42 women with early stage breast cancer, treated to the whole breast with 30 Gy in 5 weekly fractions, with or without a boost, despite the majority of women having an obese BMI⁵⁰.

Min reported a modern cohort of patients treated according to an older French trial⁵¹. 82 patients were treated to 23 Gy over 4 fractions, delivered on days 1 and 3 and 15 and 17.

Five year local control was 99%, with low rates of acute toxicity. 63 of 74 (86%) reported good or excellent cosmesis at last follow up. An included cost analysis supported substantial cost savings, compared with both standard fractionated and moderate hypofractionated schemes⁵².

Despite strong interest and rationale for study of hypofractionated radiotherapy in breast cancer, there are no data available presently on the role of hypofractionation for breast cancer with scanning beam proton therapy.³¹

The overlying hypothesis of this study is that the low α/β of breast cancer can be exploited with carefully designed hypofractionated proton therapy regimens to further optimize the therapeutic ratio, improve patient convenience, and reduce cost. The goal of this phase III randomized controlled trial is to determine whether the hypofractionated proton regimens proposed are non-inferior compared with standard fractionated proton radiotherapy and therefore worthy of further investigation.

1.4

Rationale for Doses Selected

As described above, a linear quadratic model can be used to define the alpha-beta of the normal structures and tumor as well biologic effective doses. Plausible population averaged radiobiologic parameters for breast cancer (95% confidence level) are $\alpha/\beta =$

2.88 (0.75–5.01) Gy; $a = 0.08 \pm 0.02 \text{ Gy}^{-1}$; potential doubling time $T_d = 14.4 \pm 7.8$ day.⁴³ The fractionation regimens in table 1 (modified from Qi et al.)⁴³ is based on the fitting of clinical data including the hypofractionated randomized trials mentioned above and justifies the five fraction regimen proposed for arm 2. The concurrent boost dose of 6 Gy x 5 is also based in part on the work of Formenti et al. who recently reported the 5-year results of a prospective trial of 3D-CRT APBI of 100 patients treated in the prone position to a total dose of 30Gy in 6Gy fractions. At a median follow-up of 64 months, there has been just one local recurrence and one contralateral recurrence and cosmesis was rated as good/excellent in 89% of patients with at least 36 months follow-up.⁵³ Livi et al has also shown excellent 5-year toxicity, cosmetic outcome and local failure results employing a dose of 30Gy in 5 treatments.⁵⁴ The control arm for this study will be 15 fractions based on the favorable long term follow-up of the UK START B⁵⁵. More recently the initial toxicity results of the fast forward trial have been published. Very low rates of grade 3 toxicity were seen using either the 40 Gy over 3 weeks, or 26 Gy or 27 Gy over one week.⁵⁶ It is possible that the spot proton RBE may be different than 1.1 for hypo-fractionated treatments. Trials like the currently proposed would be critical to define differences in RBE with spot scanned hypofractionated radiation as well as the cancer and normal tissue alpha/beta.

Table 1

Arms	Tx	Tumor dose 2Gy
50Gy in 2Gy	25	50Gy
45Gy in 2.26Gy	20	50Gy
33.4Gy in 3.34Gy	10	50Gy
24.7Gy in 4.98Gy	5	50Gy

2.0 Goals

2.1 Primary Objectives

2.1.1 To determine the 24-month complication rate of 5 fraction whole radiotherapy +/- concurrent boost as compared to 15 fraction radiotherapy +/- sequential boost. Complications will be defined as one or more of the following events: 1) grade 3 or higher late adverse event, 2) deterioration of cosmesis from excellent/good to fair/poor or from fair to poor.

2.2 Secondary Objectives

2.21 To evaluate acute and late toxicity
2.22 To estimate the 5-year locoregional control, invasive disease-free survival and overall survival.

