11.0 Treatment Evaluation

- 11.1 Patients will be evaluated at baseline, then according to the Assessment Schedule (Section 4.0)
- 11.2 At the time of reevaluation, patients will be classified in the following manner:
 - 11.2.1 No evidence of disease (NED).
 - 11.2.2 Recurrence of disease (REC). Consider biopsy of the site and PET scan.
 - 11.2.3 The site of recurrence (or failure) will also be collected and classified as local vs. regional vs. distant recurrence.
 - 11.2.4 Secondary Treatment. The date of the first retreatment and extent of retreatment post-recurrence (i.e. secondary resection or re-irradiation for primary disease), will be collected. Pathology, if available, and operative reports are required to be submitted per Section 18.0.
- 11.3 Cosmesis evaluation and Patient Reported Outcomes
 - 11.3.1 The Harvard/NSABP/RTOG Cosmesis Scale will be used to score cosmesis by trained nurses for the primary endpoint according to the schedule outlined in section 4.0.

Excellent: Treated breast nearly identical to untreated breast

Good: Treated breast slightly different than untreated (minimal but identifiable effects of the treated breast). Mild reddening or darkening of the breast may be present. Thickening or scar tissue causes only a mild change in the shape or size.

Fair: Obvious difference in the size and shape of the treated breast. **The change involves one-quarter or less of the breast.** Severe thickening or scarring can be present.

Poor: Marked change in appearance or shape involving **more than one-quarter or less of the breast.** Treated breast seriously distorted (severe sequelae of breast tissue)

11.3.2 Digital photographs should be performed according to the schedule outlined in section 4.0 and should include three poses: from the front with hands on hips, both oblique and lateral views with hands behind the back. Recommended framing should go from the sternal notch to the umbilicus. If possible, patients should be photographed against a solid colored background such as a white sheet.

11.3.3 The Quality of Life (QOL) questionnaires are adapted from the Breast Cancer Treatment Outcome Scale (BCTOS). PRO-CTCAE will also be used for QOL questionnaires.

11.4 Quality of life questionnaires are being done as part of the standard of care for all patients. We will correlate results of this standard of care questionnaires with clinical outcomes.

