16.0 Statistical Considerations and Methodology

- 16.1 Overview: This is an open label phase III randomized controlled trial to determine the safety of 5 fraction vs 15 fraction radiotherapy after breast conserving surgery. The goal is to determine whether the difference in 24-month complication rates between the experimental arm and the control arm is acceptable. Of interest is whether the experimental arm results in an unacceptable increase in the 24-month complication rate. If it does not, then the experimental arm will be recommended for further study. If the 24-month complication rate is found to be unacceptable, then the recommendation would be to do no further studies of the experimental arm.

- 16.2 Primary and Secondary Endpoints

16.21 Primary Endpoint: The 24-month complication rate, defined as the percentage of women evaluable at 24 months who develop one or more of the following events:

- 1) grade 3 or higher late adverse event OR
- 2) deterioration of cosmesis from excellent/good to fair/poor or from fair to poor at the 24-month evaluation (using the Harvard/NSABP/RTOG Cosmesis Scale)

16.22 Secondary Endpoints:

16.221 Acute and late adverse events including grade ≥ 2 pneumonitis.

16.223 Locoregional control, invasive disease-free, distant recurrence, disease-free survival, cause-specific survival, overall survival.

The following definitions are used for the secondary endpoints of interest:

- *Acute adverse events*: any adverse event, regardless of attribution, that occurs in the first 90 days post-RT.
- *Late adverse events* (up to 5 years post RT): any adverse event that occurred after the first 90 days post-RT and up to 5 years post-RT.
- *Ipsilateral breast tumor recurrence (IBTR)*: this is defined as local recurrence from trial registration as a first event at 5 years. IBTR is defined as both invasive and non-invasive breast cancer involving the same breast parenchyma as the original tumor.
- *Regional recurrence*: invasive breast cancer in the axilla, regional lymph nodes, chest wall, and skin of the ipsilateral breast at 5 years.
- *Distant recurrence*: metastatic cancer that has either been biopsy confirmed or clinically diagnosed as recurrent invasive breast cancer at 5 years.

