- *Invasive disease-free survival*: this is defined as the time from study registration until the occurrence of one of the events in a composite endpoint. This endpoint includes invasive IBTR, regional invasive breast cancer recurrence, distant breast cancer recurrence, death due to any cause.
- *Disease-free survival*: this is defined as the time from study registration until the occurrence of one of the events in a composite endpoint. This endpoint includes any IBTR, regional invasive breast cancer recurrence, distant breast cancer recurrence, death due to any cause,
- *Cause specific survival*: is defined as the time from registration to death due to breast cancer. If the cause of death is unknown or difficult to establish patients with a distant failure at the time of death would be censored as dying from breast cancer
- *Overall survival*: is defined as the time from registration to death due to any cause.

16.3 Exploratory endpoints:

16.31 Patient self-reported cosmesis evaluate fatigue, breast pain, arm function and other patient reported outcomes.

The following definitions are used for the exploratory endpoints of interest:

- *Patient Reported Outcomes/Quality of life:* Elements of the Patient-Reported Outcomes Version of the Common Terminology Criteria for Adverse Events (PRO-CTCAE) will be used for patient self-reporting of toxicities. The Breast Cancer Treatment Outcomes Scale (BCTOS) will be used to measure patient reported functional status (pain, mobility). Other measures of fatigue, pain, and arm function are listed in the appendix.
- *Patient self-reported cosmetic outcomes:* the patient self-reported outcome will be assessed using a modified Harvard Cosmesis Scale and the BCTOS at baseline, 2 years, and 5 years.
- *Panel assessed cosmetic outcome:* in addition to patient self-reported and physician reported outcomes, cosmesis will be assessed by a panel of breast cancer medical providers using digital photographs from baseline and at 2 years. The Panel will be blinded to treatment allocation.

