16.6 Analysis Plan

The analysis for this trial will commence at the planned time points and at the time the patients have become evaluable for the primary endpoint.

16.6.1 Primary Analysis: The primary analysis will be to estimate the difference in the complication rate (adverse cosmesis and grade 3+ toxicities) which is defined as the 24-month complication rate in experimental arm minus that in the control arm. All patients meeting the eligibility criteria who have signed a consent form and started treatment will be in the primary analysis. The complication rate will include all women evaluable at 24 months. Those who have recurrent disease or die before 24 months will not be included in this calculation. We expect that <3% of patients will not be found eligible based on failure or death.²⁴ The complication rate will be estimated using a binomial estimator in both experimental arm

and control arm, and a one-sided 90% confidence interval of the difference will be computed with normal approximation. As mentioned above, the following decisions will be made based on the 90% CI:

- ***The upper bound of the 1-sided 90% CI of the difference lies below 15%:*** The experimental arm regimen is acceptable.
- ***The upper bound of the 1-sided 90% CI of the difference lies above 15%:*** The experimental arm regimen is unacceptable.

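### Invasive disease-free and disease-free survival leave out new contralateral breast cancer, a radiotherapy harm the protocol itself names; a cheap correction to two secondary endpoints

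*Combined protocol and SAP*

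**What the plan says.** Section 2.2 (2.22) sets the objective: "To estimate the 5-year locoregional control, invasive disease-free survival and overall survival". Section 16.22 lists the secondary disease endpoints as "Locoregional control, invasive disease-free, distant recurrence, disease-free survival, cause-specific survival, overall survival". DFS is therefore a secondary endpoint too, although objective 2.22 does not name it.

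The definitions in 16.22 are closed lists:

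- iDFS: "This endpoint includes invasive IBTR, regional invasive breast cancer recurrence, distant breast cancer recurrence, death due to any cause".
- DFS: "This endpoint includes any IBTR, regional invasive breast cancer recurrence, distant breast cancer recurrence, death due to any cause".

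The same section limits each recurrence component. Ipsilateral breast tumor recurrence (IBTR) is confined to the breast that held the original tumor. Regional recurrence is confined to the axilla and regional nodes, the chest wall and the skin of the treated breast. Distant recurrence means metastatic disease. Sections 16.624 and 16.625 restate both endpoints as recurrence or death.

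For data collection, section 11.2 offers two states, no evidence of disease or recurrence, and 11.2.3 adds: "The site of recurrence (or failure) will also be collected and classified as local vs. regional vs. distant recurrence".

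Among the harms of treatment, section 1.1 says: "Radiotherapy is also associated with increased risk of contralateral breast carcinoma".

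**The concern.** An endpoint called invasive disease-free survival will be read as the proportion of women alive without invasive breast cancer. Under 16.22, a woman alive at 5 years with a new invasive cancer in the other breast is in that proportion. The protocol itself identifies this cancer as a consequence of the treatment under study, and no disease endpoint counts it.

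Data capture has the same gap. With only local, regional and distant as classes, a site has no correct place to enter the event. If the definition were widened later, cases would have to be found in free text or adverse event reports.

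At stake are the face value of two secondary estimates and a clean record of a named late harm. The trial's decision is not at stake.

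**Working it through.** **1. Can a new contralateral cancer enter through any listed component?**

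| Component in 16.22 | Scope | New contralateral cancer, woman alive |
|---|---|---|
| IBTR | Breast of the original tumor | No |
| Regional recurrence | Axilla and regional nodes, chest wall, skin of treated breast | No |
| Distant recurrence | Metastatic breast cancer | No, it is a new primary |
| Death, any cause | Death | Only if she dies |

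Sections 16.624 and 16.625 (recurrence or death) do not widen this. The omission is confirmed from the text alone.

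**2. Is it captured elsewhere?** Section 10.5 requires grade 3 to 5 adverse events outside the solicited list to be submitted regardless of attribution, and 16.622 summarises late adverse events by type, maximum grade and arm. A contralateral cancer graded 3 or higher may appear there. It still would not be an iDFS or DFS event.

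**3. The plan's own figures.** The plan gives no projected iDFS or DFS rate. Its only sizing figure is for the 24-month complication rate (16.4 and 16.5: 10% in both arms, margin 15 points, one-sided alpha 0.05, 80% power):

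n per arm = (1.645 + 0.842)² × 2 × 0.10 × 0.90 / 0.15² = 49.5, so 50 per arm and 100 evaluable.

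This reproduces the plan, and no disease endpoint enters it.

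**4. Expected omitted events by 5 years in 110 women.**

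*From the documents.* Section 1.4 cites a series of 100 partial-breast patients with a median follow-up of 64 months: "there has been just one local recurrence and one contralateral recurrence". Scaled linearly to 60 months:

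110 × 1/100 × 60/64 = 1.03 women, or 1.03/110 = 0.9 percentage points.

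*From assumed rates.* The documents give no annual rate. With r assumed at 0.2 to 0.6% per year, expected events = 110 × (1 − exp(−5r)). The last column assumes a 5-year iDFS of 95% under the current definition and independent events, so that iDFS falls by 0.95 × (1 − exp(−5r)).

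| r per year (assumed) | 5-year probability | Women in 110 | Fall in iDFS, points |
|---|---|---|---|
| 0.2% | 1.0% | 1.1 | 0.9 |
| 0.4% | 2.0% | 2.2 | 1.9 |
| 0.6% | 3.0% | 3.3 | 2.8 |

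One woman is 1/55 = 1.8 points in a single arm.

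**5. Events before 24 months, the only ones that could touch the primary analysis.**

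- From the cited series: 110 × 1/100 × 24/64 = 0.4 women.
- From the assumed rates: 110 × (1 − exp(−2 × 0.002)) = 0.4, and 110 × (1 − exp(−2 × 0.006)) = 1.3.

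These are totals over both arms.

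**The case against.** The strongest reply is that 16.22 is explicit, 16.624 and 16.625 agree with it, and a sponsor may choose its composite. That stands in part: the documents do not contradict themselves. A reader might infer a contradiction because section 1.4 speaks of a contralateral recurrence, but that sentence describes another group's series and defines nothing for this trial. What remains is that the composite leaves out a disease event the protocol names as a harm, under a name that suggests it is included.

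It can also be said that such events are not lost. That is right as far as it goes: death from the cancer counts in iDFS, DFS and overall survival, and late adverse event reporting may catch a grade 3 or higher case. A reader might infer that the event counts for nothing, and the documents do not support that.

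A reader might also infer that the primary result is at risk, because 16.6.1 says: "Those who have recurrent disease or die before 24 months will not be included in this calculation". If a site coded a contralateral cancer as recurrence, the woman would drop out of the 24-month rate. But a new primary meets none of the recurrence definitions, so this would be a coding error. It would concern about 0.4 to 1.3 women in the whole trial, and nothing in the documents suggests that it would differ by arm.

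The size is also fragile. The one documentary input is a single event, not stated to be invasive, in a partial-breast series. Section 1.1 describes breast radiotherapy in general; the documents do not say that this risk differs between 5 and 15 fractions or appears within 5 years. Section 7.88 sets no dose constraint for the contralateral breast but does ask that dose to it be limited. All of this stands, and it keeps the point small.

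**Conclusion.** The point holds as an inexpensive improvement to two unpowered secondary endpoints. As written, a woman alive with a new invasive cancer in the other breast is invasive disease-free and disease-free, and 11.2 has no class for the event.

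Five-year iDFS is overstated by roughly 1 point (about 1 woman in 110), on one event in a 100-patient series scaled linearly in time. It could reach about 3 points (3.3 women) if a rate of up to 0.6% per year is assumed. The sample size, the primary endpoint and the decision rule do not change.

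The conclusion is limited to contralateral breast cancer. Section 1.1 also names ipsilateral lung cancer, and a reader might infer that every second cancer must enter the composites. The documents give no rate for these and do not settle whether a non-breast cancer belongs in a breast cancer disease-free endpoint. That choice is the sponsor's; a tabulation by arm is enough to keep the information.

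**What to change.** - **16.22, 16.624 and 16.625:** add contralateral invasive breast cancer to iDFS, and contralateral breast cancer, invasive or in situ, to DFS. Use the same event list in all three places.
- **11.2.3 and status reporting:** add the classes *contralateral breast* and *second primary*. Keep both distinct from recurrence, so that the code alone does not trigger the exclusion in 16.6.1.
- **16.622:** tabulate second primary cancers by arm with the late adverse events. Women alive with a non-breast second cancer would remain disease-free under the revised composites, and the text should say so.

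No blanket rule that such a woman keeps her 24-month cosmesis assessment is proposed. The scale in 11.3.1 compares the treated with the untreated breast, and treatment of the other breast can remove that comparator.

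The cost is a few lines of wording and added categories in status reporting. It needs no new visits and no change to treatment or sample size. The downside is that iDFS and DFS become slightly less favourable. The classes are best added before events occur, so that cases need not be reconstructed later.
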